7.1.5. Serious Adverse Events

7.1.5.1. Definition of a Serious Adverse Event

A serious adverse event is an adverse event occurring at any dose that results in any of the following outcomes or actions:

- results in death

- is life-threatening adverse event (ie, the patient was at risk of death at the time of the event); it does not refer to an event which hypothetically might have caused death if it were more severe

- requires inpatient hospitalization or prolongation of existing hospitalization, which means that hospital inpatient admission or prolongation of hospital stay were required for treatment of an adverse event, or that they occurred as a consequence of the event

Hospitalizations scheduled before the patient signed the informed consent form will not be considered serious adverse events, unless there was worsening of the preexisting condition during the patient's participation in this study.

- results in persistent or significant disability/incapacity (refers to a substantial disruption of one's ability to conduct normal life functions)
- is a congenital anomaly/birth defect
- an important medical event that may not result in death, be life-threatening, or require hospitalization, but may jeopardize the patient and may require medical intervention to prevent one of the outcomes listed in this definition

Examples of such events are intensive treatment in an emergency room or at home for allergic bronchospasm; blood dyscrasias or convulsions that do not result in hospitalization; or the development of drug dependency or drug abuse. Note: Any suspected transmission of an infectious agent via a medicinal product is considered an important medical event.

An adverse event that does not meet any of the criteria for seriousness listed above will be regarded as a nonserious adverse event.

7.1.5.2. Expectedness

A serious adverse event that is not included in the Adverse Reaction section of the relevant reference safety information (RSI) by its specificity, severity, outcome, or frequency is considered an unexpected adverse event. The RSI for this study is the US prescribing information for reslizumab and for FDG.

7.1.5.3. Reporting a Serious Adverse Event

7.1.5.3.1. Investigator Responsibility

To satisfy regulatory requirements, all serious adverse events (as described in Section 7.1.5.1) that occur during the study period (including the protocol-defined follow-up period, described in Section 7.1.2), regardless of judged relationship to treatment with the study drug, must be reported to the sponsor by the investigator. The event must be reported within 24 hours of when the investigator learns about it. Completing the serious adverse event form and reporting the event must not be delayed, even if not all the information is available. The investigator does not need to actively monitor patients for adverse events once this study has ended.

Serious adverse events occurring to a patient after the treatment of that patient has ended should be reported to the sponsor if the investigator becomes aware of them.

The serious adverse event form should be sent to the local safety officer (LSO) or (contact information is in the Clinical Study Personnel Contact Information section); the LSO will forward the report to the sponsor's Global Patient Safety and Pharmacovigilance.

The following information should be provided to record the event accurately and completely:

- study number
- investigator and investigational center identification
- patient number
- onset date and detailed description of adverse event
- investigator's assessment of the relationship of the adverse event to the study drug (no reasonable possibility, reasonable possibility)

Additional information may include the following:

- age and sex of patient
- date of first dose of study drug
- date and amount of last administered dose of study drug
- action taken
- outcome, if known
- severity
- explanation of assessment of relatedness
- concomitant medication (including doses, routes of administration, and regimens) and treatment of the event
- pertinent laboratory or other diagnostic test data
- medical history
- results of dechallenge/rechallenge, if known
- for an adverse event resulting in death:
 - cause of death (whether or not the death was related to study drug)
 - autopsy findings (if available)

The investigator must ensure that the IEC/IRB is also informed of the event, in accordance with national and local regulations.

Each report of a serious adverse event will be reviewed and evaluated by the investigator and the sponsor to assess the nature of the event and the relationship of the event to the study drug, study procedures, and to underlying disease.

Additional information (follow-up) about any serious adverse event unavailable at the initial reporting should be forwarded by the investigator within 24 hours of when it becomes known to the same address as the initial report.

For all countries, the sponsor's Global Patient Safety and Pharmacovigilance will distribute the Council for International Organizations of Medical Sciences form/Extensible Markup Language file to the LSO for submission to the competent authorities, IEC/IRBs, and investigators, according to regulations. The investigator is responsible for ensuring that the IEC/IRB is also informed of the event, in accordance with national and local regulations.

Blinding will be maintained for all clinical study personnel. Therefore, in case of a SUSAR, only the LSO will receive the unblinded report for regulatory submission; the others will receive a blinded report.

Note: Although pregnancy is not a serious adverse event, the process for reporting a pregnancy is the same as that for reporting a serious adverse event, but using the pregnancy form (see Section 7.2).

7.1.5.3.2. Sponsor Responsibility

If a serious unexpected adverse event is believed to be related to the study drug or study procedures, the sponsor will take appropriate steps to notify the appropriate competent authorities (and IEC/IRB, as appropriate).

In addition to notifying the investigators and competent authorities (and IEC/IRB, as appropriate), other measures may be required, including:

- altering existing research by modifying the protocol
- discontinuing or suspending the study
- altering the process of informed consent by modifying the existing consent form and informing all study participants of new findings
- modifying listings of expected toxicities to include adverse events newly identified as related to reslizumab.

7.1.6. Protocol-Defined Adverse Events for Expedited Reporting to Teva

For the purposes of this protocol, the following are considered protocol-defined adverse events for expedited reporting to Teva: anaphylaxis, newly-diagnosed malignancy, and parasitic helminth and opportunistic infections. Protocol-defined adverse events for expedited reporting can be either serious or nonserious according to the criteria outlined in Section 7.1.5.1. The process for reporting a protocol-defined adverse event for expedited reporting is the same as that for reporting a serious adverse event (see Section 7.1.5.3).

7.1.7. Specific Adverse Event Case Report Form Capturing

7.1.7.1. Anaphylaxis/Hypersensitivity Reactions Case Report Form

Information about all suspected anaphylaxis events will be recorded on the Suspected Anaphylaxis/Hypersensitivity Reactions CRF, which is based on the 2006 Joint NIAID/FAAN Second Symposium on Anaphylaxis (Sampson et al 2006, Appendix C). The Anaphylaxis/Hypersensitivity Reactions CRF should be initiated in real time (along with vital sign assessment) for events occurring after study drug administration in the clinic or as soon as possible for suspect events outside the clinic.

Blood samples for ADA testing should be taken in any case where hypersensitivity is suspected to be related to study drug/placebo administration.

7.1.7.2. Creatine Phosphokinase/Muscular Adverse Events Case Report Form

Potentially clinically significant CPK elevations (with or without associated symptoms) or myalgia/muscle symptoms will be recorded as an adverse event and documented using the potentially clinically significant CPK/myalgia case report form. A potentially clinically significant CPK is defined as $\geq 3.1 \times$ ULN (Grade 3 based on the FDA “Guidance for Industry Toxicity Grading Scale for Healthy Adult and Adolescent Volunteers Enrolled in Preventative Vaccine Clinical Trials”).

7.1.8. Withdrawal Due to an Adverse Event

Any patient who experiences an adverse event may be withdrawn from the study or from study treatment at any time at the discretion of the investigator. If a patient is withdrawn wholly or in part because of an adverse event, both the adverse events page and termination page of the CRF will be completed at that time.

The patient will be monitored at the discretion of the investigator (eg, until the event has resolved or stabilized, until the patient is referred to the care of a health care professional, or until a determination of a cause unrelated to the study drug or study procedure is made). The investigator must inform the Sponsor’s Authorized Representative as soon as possible of each patient who is being considered for withdrawal due to adverse events. Additional reports must be provided when requested.

If a patient is withdrawn from study for multiple reasons that include adverse events, the termination page of the CRF should indicate that the withdrawal was related to an adverse event. An exception to this requirement will be the occurrence of an adverse event that in the opinion of the investigator is not severe enough to warrant discontinuation but that requires the use of a prohibited medication, thereby requiring discontinuation of the patient. In such a case, the reason for discontinuation would be need to take a prohibited medication, not the adverse event.

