5.3. Prior and Concomitant Medication or Treatment

Any prior or concomitant medication, treatment, or procedure a patient has had within 4 weeks before screening and up to the end of study period, including follow-up, will be recorded on the CRF. Generic or trade name, indication, and dosage will be recorded. The sponsor will encode all therapy and medication according to the World Health Organization drug dictionary.

- Patients should refrain from using reliever inhalers for 6 hours before any study visit that includes spirometry or airway reversibility testing, including the screening visit.
- If a patient is taking LABAs, these should be withheld for 12 hours before any study visit that includes spirometry or airway reversibility testing, including the screening visit.

The following medications will not be allowed during this study:

- Any immunosuppressive or immunomodulatory agents (biological and non biological), including, but not limited to systemic steroids, methotrexate, cyclosporine, and interferon (excluding maintenance allergen immunotherapy)

- All biologic therapies, including, but not limited to omalizumab (Xolair®), mepolizumab (Nucala), benralizumab, lebrikizumab, and anti-tumor necrosis factor monoclonal antibodies
- All nonbiologic investigational drugs
- Inhaled nicotine (including electronic cigarettes)

The following medications are allowed as *prior medications*, with the restrictions as noted:

- Treatment with systemic corticosteroids must have been stopped at least 6 weeks prior to the Part 1 baseline visit
- Treatment with systemic immunosuppressive, immunomodulating, or other biologic agents (including, but not limited to, anti-IgE mAb, methotrexate, cyclosporin, interferon- α , or anti-tumor necrosis factor mAb) must have been stopped at least 6 months prior to screening
- Baseline asthma therapy regimen (including, but not limited to, inhaled corticosteroids, leukotriene receptor antagonists, 5-lipoxygenase inhibitors, or cromolyn) must be stable for 30 days prior to screening and judged by their treating physician to be able to continue without dosage changes throughout the study.

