9.7.2. Safety Analysis

All adverse events will be coded using the Medical Dictionary for Regulatory Activities. Each patient will be counted only once in each preferred term or system organ class category for the analyses of safety. Summaries will be presented for all adverse events (overall and by severity). Patient listings of serious adverse events and adverse events leading to withdrawal will be presented.

Changes in laboratory and vital signs measurement data will be summarized descriptively.

The use of concomitant medications will be summarized by therapeutic class using descriptive statistics. Concomitant medications will include all medications taken while the patient is treated with study drug.

Newly occurring abnormalities in the physical examinations will be identified and listed.

For continuous variables, descriptive statistics (n, mean, standard deviation, median, minimum, and maximum) will be provided for actual values and changes from baseline to each time point. For categorical variables, patient counts and percentages will be provided. Descriptive summaries of serious adverse events, patient withdrawals due to adverse events, and potentially clinically significant abnormal values (clinical laboratory or vital signs) based on predefined criteria will be provided as well.

If any patient dies during the study, a listing of deaths will be provided and all relevant information will be discussed in the patient narrative included in the CSR.

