11.1.2. Protocol Violations

Any deviation from the protocol that affects, to a significant degree, (a) the safety, physical, or mental integrity of the subjects of the study and/or (b) the scientific value of the study will be considered a protocol violation. Protocol violations may include non-adherence on the part of the patient, the investigator, or the sponsor to protocol-specific inclusion and exclusion criteria, primary objective variable criteria, or GCP guidelines; noncompliance to study drug administration; use of prohibited medications. Protocol violations will be identified and recorded by investigational center personnel in the CRF. All protocol violations will be reported to the responsible IEC/IRB, as required.

When a protocol violation is reported, the sponsor will determine whether to discontinue the patient from the study or permit the patient to continue in the study, with documented approval from the medical expert. The decision will be based on ensuring the safety of the patient and preserving the integrity of the study.

Changes in the inclusion and exclusion criteria of the protocol are **not** prospectively granted by the sponsor. If investigational center personnel learn that a patient who did not meet protocol inclusion and exclusion criteria was entered in a study, they must immediately inform the sponsor of the protocol violation. If such patient has already completed the study or has withdrawn early, no action will be taken but the violation will be recorded.

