### **8.2. Adverse Events**

All adverse events will be coded using the latest available version of the Medical Dictionary for Regulatory Activities (MedDRA), associated with five levels of classifications: a System Organ Class (SOC), a High Level Group Term (HLGT), a High Level Term (HLT), a Preferred Term (PT) and a lowest Level Term (LLT).

Only Treatment Emergent Adverse Event (TEAE), defined as events occurring after the first drug administration and until the end of the study, will be presented, based on Safety analysis set.

Similarly, AEs occurring between ICF signing and end of Part 1 will be presented based on Enrolled analysis set.

In the AE summary tables each patient will be counted only once in each preferred term or system organ class category for the analyses of safety. Summaries will be presented for all adverse events by treatment group, and overall as following:

- All AEs sorted by SOC and PT based on Safety analysis set (Summary 15.3.1.1) and on Enrolled analysis set (Summary 15.3.1.2)
- All AEs sorted by PT based on Safety analysis set (Summary 15.3.1.3) and on Enrolled analysis set (Summary 15.3.1.4)
- Treatment-related AE sorted by SOC and PT based on Safety analysis set (Summary 15.3.1.5)
- Serious AE sorted by SOC and PT based on Safety analysis set (Summary 15.3.1.6)
- Non serious AE sorted by SOC and PT based on Safety analysis set (Summary 15.3.1.7)
- AE sorted by SOC, PT and severity based on Safety analysis set (Summary 15.3.1.8).

Asthma deterioration will be descriptively summarized for safety analysis set (Summary 15.3.1.9).

Patient listings of serious adverse events and adverse events leading to withdrawal will be presented. Suspected anaphylaxis/hypersensitivity and CPK reactions will be listed individually (Listings 16.2.8.12 and 16.2.8.13).

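### Under a narrow coding exception, some withdrawals set off by an adverse event are recorded as due to a prohibited medication, so they can be missed in the count of withdrawals due to adverse events

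*Protocol*

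**What the plan says.** Protocol 7.1.8 starts with an inclusive rule. If a patient leaves for several reasons and one is an AE, "the termination page of the CRF should indicate that the withdrawal was related to an adverse event". It then carves out one situation: an AE that the investigator considers "not severe enough to warrant discontinuation but that requires the use of a prohibited medication, thereby requiring discontinuation of the patient". For that situation the instruction is: "In such a case, the reason for discontinuation would be need to take a prohibited medication, not the adverse event".

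The prohibited list in Protocol 5.3 covers immunosuppressive and immunomodulatory agents, "including, but not limited to systemic steroids".

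Three kinds of output depend on how a withdrawal is attributed:

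- Protocol 9.4.1 and SAP 5.2 tabulate withdrawals by reason.
- Protocol 9.7.2 plans "Descriptive summaries of serious adverse events, patient withdrawals due to adverse events", among other summaries.
- Protocol 9.7.2 also plans a listing, which SAP 8.2 repeats: "Patient listings of serious adverse events and adverse events leading to withdrawal will be presented".

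Neither document defines when an AE counts as leading to withdrawal, and neither names the data field behind the summary or the listing.

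**The concern.** In the excepted situation the protocol's own chain runs from AE to medication to discontinuation. Without the event there would have been no medication and no withdrawal. The termination page nevertheless names only the middle link. This departs from the inclusive rule stated just before it, and it moves cases in one direction only: out of the AE category, never into it.

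Whether the exception applies also rests on the investigator's opinion about severity, so two similar events could be coded differently. At stake is a safety figure that readers look at early, how many patients left because of an AE, in a trial where each arm has about five patients.

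**Working it through.** The plan states no figure to reproduce. The check follows the coding rule into the outputs and looks for anything that would bring the recoded cases back.

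1. **Who is caught.** Both conditions in 7.1.8 must hold: the event is judged insufficient by itself to warrant discontinuation, and it needs a prohibited medication that ends participation. An AE judged sufficient by itself stays under the inclusive rule.

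2. **Asthma worsening is mostly elsewhere.** Protocol 3.12 requires termination after an exacerbation in Part 2. Protocol 7.1.1 records worsening asthma as an AE only if it is more severe than would be expected for that patient. The exception therefore bears mainly on non-asthma events treated with, for example, systemic steroids.

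3. **Outputs built on the recorded reason.** In the disposition tables the patient still counts as withdrawn, but under the medication. A 9.7.2 summary drawn from the same reason omits the patient. The effect on these outputs is direct.

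4. **The listing.** Its source is not stated, so the effect is an inference. The AE items required by Protocol 7.1.2 include action on study drug, treatment given and outcome; no item for withdrawal from the study is named. With a single infusion, action on study drug says little about a later withdrawal. In Protocol 4.4, the instruction to record the specific event applies when the reason for withdrawal is an AE or a significant laboratory abnormality, and under the exception the stated reason is neither. The termination page is thus the only link from AE to withdrawal that the documents describe.

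5. **Recapture.** No passage in either document adds these cases back to the count.

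6. **Weight of one case.** With n dosed patients in an arm, one recoded patient lowers the arm's proportion by 1/n.
   - n = 5 (planned, Protocol 9.1): 1/5 = 20 percentage points, for example 1/5 reported as 0/5.
   - n = 6 (one replacement dosed in that arm): 1/6 = 16.7, about 17 points.
   - Both arms together, planned: 1/10 = 10 points.

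   The n = 6 case is realistic. Protocol 3.12 enrols further patients after exacerbation terminations until ten have completed all three post-dose scans, and the safety set in Protocol 9.2.2 keeps everyone dosed.

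7. **Direction.** Within an arm the change is always downward. The difference between arms can move either way, depending on which arm the recoded patient is in.

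**The case against.** The strongest reply is that this is a prespecified attribution convention of limited reach, and that nothing is hidden. The AE remains in the general AE tables. The AE page records the treatment given, and concomitant medications are recorded with their indication (Protocol 5.3). Use of a prohibited medication may be a protocol violation, which SAP 5.8 summarises and lists. SAP 8.1 promises individual listings. With about ten treated patients, a reader could piece the sequence together. All analyses are descriptive and the primary endpoint is untouched.

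Most of this stands, and it sets the size of the point. It does not remove it: a sequence that can be traced across separate listings does not correct the reported count.

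The reply also rules out several stronger readings that a reader might infer:

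- **That every AE needing a prohibited medication is recoded.** The severity condition in 7.1.8 excludes this.
- **That serious drug reactions disappear.** Protocol 1.4.1.2 names severe systemic reactions as a risk, but the exception covers only events judged not severe enough to warrant discontinuation. Suspected anaphylaxis or hypersensitivity has its own case report form (Protocol 7.1.7.1), and SAP 8.2 lists these reactions and CPK reactions individually.
- **That the SAP 8.2 listing certainly omits these cases.** Its source field is not given. SAP 8.2 also specifies no summary table of AE withdrawals; that summary rests on Protocol 9.7.2 alone.
- **That 7.1.8 flatly contradicts 11.1.2.** Section 7.1.8 describes discontinuation as required once the medication is needed. Section 11.1.2 counts prohibited-medication use among possible violations, after which "the sponsor will determine whether to discontinue the patient from the study or permit the patient to continue in the study". Section 7.1.10 has the investigator decide on continuation in consultation with the sponsor. One can read 7.1.8 as saying only what to record once a patient has been discontinued. The passages need aligning, but they are not irreconcilable.

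**Conclusion.** The concern holds in a narrow form. For AEs judged insufficient by themselves to warrant discontinuation, but whose treatment ends participation, the recorded reason leaves out the AE. Outputs built on that reason would understate withdrawals due to AEs; the AE-withdrawal listing would probably do so too. The loss is one of attribution, not of the events.

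The number of affected patients is unknown and may be 0. Each one lowers an arm's proportion by up to 20 percentage points, or about 17 with six in the arm. This rests on two assumptions: that each arm reaches at least its planned five dosed patients, and that the Protocol 9.7.2 summary is drawn from the recorded reason. The 20 points are not a fixed amount per case, because replacement enrolment can enlarge an arm. This is a safety-reporting correction worth making; it does not affect the efficacy results.

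**What to change.** 1. On the termination page, record both the AE and the need for a prohibited medication as reasons. If the sponsor prefers to keep the present wording of 7.1.8, add instead a flag on the AE page for any AE whose occurrence or treatment led to withdrawal from the study.
2. In SAP 8.2, define an AE leading to withdrawal as any AE recorded as a whole or partial reason, or whose treatment led to the withdrawal. Name the source field, and use the definition for both the Protocol 9.7.2 summary and the listing.
3. Leave the clinical withdrawal rule unchanged. Ask the sponsor to reconcile the wording of 7.1.8, which presents discontinuation as required, with 7.1.10 and 11.1.2, under which continuation is decided case by case.

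The cost is one extra case report form field, one SAP definition and a small wording change in 7.1.8 if both reasons are recorded. The reported AE-withdrawal figure may become slightly less favourable.
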